#### 4.0 Research Objectives, Questions & Hypotheses

The *primary research question* is: 1) What is the optimal design (patient sample, instruments) and operational processes to assess the effects of NPW on individuals who have been diagnosed with stage I-IV NSCLC? *Secondary research questions* are: 2) How does participating in an eight-week Nordic pole walking program affect physical function, and 3) health related quality of life (HRQoL) of these individuals?

The *primary objective* is to assess the feasibility of a NPW program for individuals with stage I-IV NSCLC by establishing the optimal design and operational processes. The *secondary objectives* are to: determine the effects of NPW on 1) physical function, and 2) HRQoL.

*Hypotheses* are that the NPW program for individuals who have been diagnosed with stage I-IV NSCLC will: 1) be feasible; 2) improve physical function; and 3) improve the HRQoL.

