#### 5.0 Methods:

- 5.1 Study Design: This is an eight-week multi-centre randomized controlled pilot study to establish optimal study design and operational processes to inform a larger scale study(37, 38). The intervention group will participate in an individualized NPW program, while the control group continues their usual daily routine. The control group is necessary because it increases the reliability of the results by allowing researchers to compare the control group measurements to the intervention group measurements.

- 5.2 Location of Research:

1. Lakeridge Health, Oshawa, Ontario (n=5 intervention, n=5 control, approximate eligible population at Lakeridge is 300, this is based on current and new cases of lung cancer at the Durham Regional Cancer Centre)
2. Southlake Regional Health Centre, Newmarket, Ontario (n=5 intervention, n=5 control)
3. Abilities Centre, Whitby, Ontario (ATTACHMENT 1)
4. Magna Centre, Newmarket, Ontario (ATTACHMENT 2)

5.3 Sample Selection: The *inclusion criteria*: 1) primary diagnosis of histologically confirmed stage I-IV NSCLC (with any concurrent cancer treatment), 2) approval of primary treating physician, and 3)  $\geq 18$  years old. The *exclusion criteria*: 1) not able to communicate in English, 2) unable to consent, e.g. incapable, and 3) use of Nordic walking poles on a regular basis within the last six months. We will presume the study participant is capable with respect to the research study unless we suspect incapacity exists based on: the physician's assessment; direct observation of the person e.g., the person is confused, disoriented, depressed, psychotic, extremely anxious, unable to make a decision, intoxicated; or from information obtained from family or other caregivers.

5.4 Recruitment: We anticipate recruiting a minimum of 20 individuals with NSCLC (n=10 intervention group, n=10 control group). It is important that the pilot study be representative of the target study population(37, 38). The sample size needs to be large enough to provide useful information about the feasibility of the study(37, 38). Recruitment and enrolment will take place from approximately November 2015 – April 2016. The recruitment procedures are as follows:

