## 5.5 Outcomes:

5.5.1 *Feasibility*: The feasibility objectives for this pilot study are to:

1. verify recruitment, consent and randomisation procedures;
2. confirm the sample size required for a fully study;
3. confirm the inclusion/exclusion process;
4. test the appropriateness of assessment tools used in the study;
5. determine appropriate timing of data collection;
6. confirm that the data collection materials are sufficient;
7. monitor the operational processes; and
8. formalize the protocols for Nordic pole walking exercise prescription.

See the chart in ATTACHMENT 9 for further explanations and a more detailed list of feasibility measurements. Notes regarding the study process will be documented throughout the study. Participants upon study completion will also complete a program evaluation survey (ATTACHMENT 10) to reflect on their experience.

5.5.2 *Participant Characteristics*: Participant demographics (ATTACHMENT 11), general health history, smoking status, physical activity level (ATTACHMENT 12)(39), height, weight, girth measurements (bicep, chest, waist, hips and thigh), resting heart rate and oxygen saturation levels (ATTACHMENT 13) will be recorded to provide further understanding of the composition of the participant group.

5.5.3 *Physical Function*:

- 1) *Lower body physical function* will be measured using the 6MWT(40) and the 30-second (30-s) chair stand test(41). The 6MWT has been recognized by the American Thoracic Society as a valid measure of submaximal functional capacity in those with pulmonary disease(40). This self-paced test measures the distance that an individual can walk over a 25 or 30m track in six minutes(40). Granger et al. estimated the minimal important difference for

deterioration of the 6MWT in lung cancer to be between 22m and 42m or a change of 9.5%(42). Having a greater 6MWT distance was correlated with better function, increased physical activity and decreased dyspnea(42). The 30-s chair stand test is a valid indication of lower body strength in the older adult population(41). The test requires participants to complete as many sit to stands as possible in 30 seconds(41). The 30-s chair stand test has been used to assess lower body strength in pulmonary fibrosis patients(43) and the COPD population(44).

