- 2) *Upper body physical function* will be assessed with the unsupported upper limb exercise test (UULEX)(45, 46) and the handgrip strength test. The UULEX is a valid incremental test that has been used to measure peak unsupported arm exercise capacity in the chronic lung disease population (45, 46). The test requires the seated participant to lift a plastic bar (0.2kg) through eight levels at a constant cadence of 30 beats per minute as directed by a metronome. Once the maximum height is reached the weight of the bar is increased by 0.5kg every minute to a maximum weight of 2.0 kg. The test continues until the participant experiences fatigue and decides to stop. The results are recorded in seconds. Handgrip strength is correlated with survival, weight loss, sarcopenia and quality of life characteristics in advanced cancer patients(47, 48). As recommended by the American Society of Hand Therapists grip strength will be measured using a dynamometer with the handle in the second position. Individuals will be seated with their shoulder adducted and elbow flexed 90° and their forearm in neutral. Three successive trials for both hands will be recorded.

5.5.4 *HRQoL*: HRQoL has been shown to be a significant independent predictor of survival duration in the cancer population(49). We will assess HRQoL in NSCLC patients using the SF-36 (ATTACHMENT 14)(50) and the Functional Assessment of Cancer Therapy – Lung (FACT-L) (version 3) (ATTACHMENT 15)(51).

The SF-36 has been validated and used extensively as a measure of HRQoL(50). It assesses eight health concepts: 1) Limitations in physical activities because of health problems; 2) Limitations in social activities because of health problems; 3) Limitations in usual role activities because of health problems; 4) bodily pain; 5) general mental health (psychological distress and well-being); 6) limitations in usual role activity because of emotional problems; 7) vitality (energy and fatigue); 8) general health perceptions. The SF-36 has been used in other studies to examine HRQoL in the NSCLC population(52-55).

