## **7.0 Statistical Analysis**

Narrative descriptions will be used to address feasibility outcomes. Descriptive statistics (mean, median, standard deviation) will be calculated for any numeric data. Non-parametric tests will be used to compare the intervention and control group due to small sample size; a Wilcoxon signed-rank test to see if changes occurred over time and a Mann-Whitney U test to see if there was difference between groups. A p-value of less than 0.05 will considered significant.

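### Section 7.0 calls every p-value below 0.05 significant across several unranked efficacy measures, with no lead measure and no exploratory label (minor)

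*Combined protocol and SAP*

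**What the plan says.** Section 4.0 makes feasibility the primary objective. The secondary objectives are to "determine the effects of NPW on 1) physical function, and 2) HRQoL". The hypotheses in the same section are directional: the programme will "1) be feasible; 2) improve physical function; and 3) improve the HRQoL".

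Section 5.5 lists the measures. Physical function has four: the 6MWT, the 30-second chair stand, the UULEX and handgrip, with grip recorded in both hands. HRQoL has two questionnaires. Of the SF-36 the protocol says "It assesses eight health concepts", and it describes the FACT-L as having five dimensions.

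Section 7.0 describes feasibility outcomes narratively. For the numeric outcomes it plans "a Wilcoxon signed-rank test to see if changes occurred over time" and "a Mann-Whitney U test to see if there was difference between groups", and then adds "A p-value of less than 0.05 will considered significant". It does not say which scores are tested or which measure leads within either domain. Nor does it say how many results would be needed to support hypothesis 2 or 3, or whether the p-values are exploratory.

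**The concern.** A directional hypothesis with several measures and a bare per-test threshold leaves open, until the data are seen, what would count as support. If one score of many falls below 0.05, the plan allows it to be called significant, and nothing stops it being presented as support for hypothesis 2 or 3. The more scores are tested, the more likely such a result is by chance alone.

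What is at stake is how the pilot is read. Section 5.1 says the study is to inform a larger one, and Section 9.0 plans summaries for patients and providers. An isolated significant score could be taken there as evidence of benefit.

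**Working it through.** The plan states no family-wise error rate, power or sample-size calculation, so there is no figure of its own to reproduce beyond the per-test 0.05.

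**Inputs from the documents.** Section 5.4 gives the sample size: "We anticipate recruiting a minimum of 20 individuals with NSCLC (n=10 intervention group, n=10 control group). The between-arm test is Mann-Whitney and the threshold is p<0.05. Two-sidedness and the exact version of the test are assumed, because neither is stated.

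**Number of tests (assumed).** Four function tests, eight SF-36 concepts and five FACT-L dimensions give 4 + 8 + 5 = 17. Counting each hand separately, or adding a FACT-L total, gives 18; doing both gives 19. A sparser reading, with four function tests and one total per questionnaire, gives 4 + 2 = 6.

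**Size of one test.** With 10 per arm the exact two-sided Mann-Whitney test rejects at U ≤ 23 (or, in the other tail, U ≥ 77). Its true size is 0.0433, or 0.0216 in the direction favouring NPW.

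**Independent outcomes.** The chance of at least one false positive in k tests is 1 − (1 − size)^k.

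- 18 tests: 1 − 0.9567^18 = 0.549. Favouring NPW only: 1 − 0.9784^18 = 0.325.
- 6 tests: 1 − 0.9567^6 = 0.233. Favouring NPW only: 1 − 0.9784^6 = 0.123.

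**Correlated outcomes.** These come from simulation under no effect, with 10 per arm, normal outcomes and equal correlation between scores.

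| Correlation (assumed) | 18 tests, either direction | 18 tests, favouring NPW | 6 tests, either direction | 6 tests, favouring NPW |
|---|---|---|---|---|
| 0 | 55% | 32% | 23% | 12% |
| 0.5 | 38% | 19% to 20% | 19% | about 10% |
| 0.7 | 27% to 28% | 14% | 15% | 8% |

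**Sensitivity.** With 17 to 19 tests the either-direction figure is 53% to 57% if independent and 27% to 29% at correlation 0.7. With 18 tests at correlation 0.8 it is 22%. If the large-sample version of the test is used without continuity correction, 18 tests give about 32% (correlation 0.7) to 62% (correlation 0).

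**Not counted.** The within-arm Wilcoxon tests are left out. With 18 scores they would add two per score, making 18 × 3 = 54 p-values. They do not compare the arms, and a change over time in one arm need not be an effect of the programme.

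**The case against.** The strongest reply is that the plan sets only a per-test threshold. A reader might infer that any single p<0.05 is the stated decision rule for hypothesis 2 or 3. The documents do not say so. What stands against the plan is narrower: it offers no other rule.

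A reader might also take 27% to 55% as a property of the plan. It is not. Section 5.5 describes what the questionnaires contain and does not say that every subscale will be tested. Recording both hands does not imply two grip tests. The figure also counts results favouring control, which could not support hypotheses of improvement. The lower figures, for six scores and for results favouring NPW, are equally compatible with the text.

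The documents also limit the weight of these tests. Efficacy is secondary, feasibility is narrative, and Section 3.5 itself says that pilot studies contribute little statistically. A reader might infer that a chance result would fix the full trial's primary outcome, but no section selects that outcome by p-value. Assessing the tools is a feasibility objective, with detail in an attachment that is not part of the document reviewed.

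Finally, letting the 6MWT alone decide physical function is debatable. The protocol also measures upper-body function, for an exercise done with poles, and the 22 to 42 m important difference it quotes for the 6MWT is for deterioration. These replies lower the severity and shape the fix. They do not supply the missing lead measure or label.

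**Conclusion.** The point holds as a minor one. Section 7.0 pairs two directional hypotheses with an unqualified significance threshold over several unranked measures. The chance of at least one false positive favouring NPW ranges from about 8% (six scores, correlation 0.7) to about 32% (18 independent scores). In either direction the range is about 15% to 55%. These figures rest on assumed numbers of tests, assumed correlations, the exact two-sided test and 10 per arm. The documents fix only the last of these, and as a minimum.

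The documents do not support saying that the plan's own rule yields a wrong result. They support saying that it leaves the reading of hypotheses 2 and 3 open, with an appreciable chance of a misleading significant finding.

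**What to change.** In Section 7.0, state that the efficacy analyses of this pilot are exploratory. Report each outcome as a between-arm difference in change from baseline with a 95% confidence interval (for example Hodges-Lehmann). State that p<0.05 on any single measure will not be used to declare hypothesis 2 or 3 supported.

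If the sponsor wants a formal test, it should name one lead measure per hypothesis before data are seen and judge only those two, between arms. The 6MWT and the FACT-L total are possible choices, subject to the point about upper-body function. Two unadjusted tests still carry a chance of a false positive of 1 − 0.9567^2 = 8.5% at the exact size, or 1 − 0.95^2 = 9.75% at the nominal size, if independent. Testing each at 0.025 would hold it at or below 5%.

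The cost is a few sentences in Section 7.0, with no extra patients or data. The downside is that fewer results can be called significant.

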## **8.0 Data Management and Confidentiality**

Participants will be assigned a unique study number for the duration of the study. Only this number will be used on any research-related information collected about the participant during the course of this study, so that their identity as a participant in this study will be kept confidential. Information that contains the participant's identity will remain only with the Principal Investigator and/or designate. The list that matches the participant's name to the unique study number that is used on the research-related information will not be removed or released without the participant's consent unless required by law.

Participant information and the data collected will be kept in separate locked cabinets within [name] secure office at UOIT. The locked cabinets will require different keys for access. Furthermore, de-identified data will be stored on the laptop of the Principal Investigator ([name]), as well as one of the supervisor's laptop ([name]) and will backed up on an encrypted USB flash drive. All computerized devices used throughout this study are password protected to reinforce confidentiality.

After the data has been used for this study, it may be utilized again in a secondary use of data, but only in an aggregate way and never in a way in which the participant could be identified.

## **9.0 Knowledge Translation**

Our knowledge translation target audience are health providers and patients who have an interest in and/or actively involved in improving the effects of lung cancer. Our knowledge translation strategy is to provide this audience with a variety of products including: 1) web postings of plain language summary of results on a website designed for this study and with external organization (e.g. The Lung Association); 2) direct dissemination of summary of results (web, social media, brochures); 3) presentations and workshops at relevant clinical conferences (e.g. Canadian Respiratory Conference); and 4) publishing in a peer-reviewed publications.

## **10.0 Timeline**

Task	Months (May 2015 – July 2016)											
	S	O	N	D	J	F	M	A	M	J	J	
Committee Meetings			X			X						
Ethics Applications	X	X										
Prepare Tracking Sheets & Manual	X	X										
Recruit Patients			X	X	X							
Training Research Personnel		X	X									
Data Collection			X	X	X	X	X	X				
Data Analysis							X	X	X			
Write-up								X	X	X		
Presentations								X	X			
Submit Thesis										X		
Defend Thesis												X

